#### **Staff Training and Certification**

All staff involved in conducting the clinical trial will undergo training and be certified on the use, safety, and clinical procedures of the invisa-RED Technology Elite.

### **Data Analysis and Data Monitoring**

The measured weight loss and total inches lost per participant from the two groups will be statistically evaluated using an Independent T-Test with a P value of .05.

The study is classified as a minimal risk trial of short duration therefore a detailed plan for monitoring the data for participant safety is not required.

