## Purpose of the Study

The trial is designed to provide the empirical data to compare the efficacy and safety of the invisa-RED Technology Elite Low-level Laser Therapy (LLLT) device with a sham device when used in the treatment of individuals for weight loss and aesthetics. At the conclusion of the trial; the change in body fat percentage, and the weight and inches lost of the two groups will be statistically analyzed to determine the efficacy of the invisa-RED Technology Elite in weight loss and/or aesthetics therapy.

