#### **Methods and Procedures**

The trial is designed to prove the efficacy and safety of the invisa-RED Technology Elite Low-level Laser Therapy (LLLT) device. The trial will compare results between two groups; the first will be treated using a fully functional invisa-RED Technology Elite device; this group will be internally designated the Usual Care Group. The second, a control group, will be treated utilizing a nonfunctional invisa-RED Technology Elite device; this group will be referred to internally as the Sham Group.

The sham device will consist of an invisa-RED Technology Elite device that will appear to operate as the Usual Care Group device to the operator, but the laser diodes will be disabled and will receive no power. If staff or a participant questions the efficacy of the sham device, an assertion may be made that only a near infrared, nonvisible frequency of light, is being employed.

The trial will be conducted employing a double blind study methodology; participants will be randomly assigned to each group through a drawing, neither participants nor clinicians will know to which trial group they are assigned. To ensure the double blind; treatment for the two groups will occur on separate days of the week. All participants will receive therapy at the [name] Chiropractic Center located in Hixson, TN. Group 1 will be assigned Monday, Wednesday, Friday, and Group 2; Tuesday, Thursday, and Saturday. Additionally staff administering the trial therapy will be assigned to work with one (1) group exclusively.

A simplified weight loss protocol will be employed based on the "Consultation Protocol" from the invisa-Red Training Manual. All study participants will undergo nine (9) therapy sessions of 20 minutes each; using a singular protocol setting for pulse (3.5s) and delay (0.2s), but power settings will be based on the participants Fitzpatrick Scale skin type. For skin types i and ii a power setting of 7 will be used, for skin types iii and iv a power setting of 6, for skin types v and vi a power setting of 4 will be employed. At the conclusion of the nine (9) therapy sessions; the change in body fat percentage, weight, and inches lost of the two groups will be statistically analyzed to determine the efficacy of the invisa-RED Technology Elite as a weight loss therapy. Any medical errors will be included in the statistical analysis.

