Statistical Analysis Plan

Cover Page

for the Clinical Study

"Comparing the Efficacy of a Dual-Frequency Laser-Emitting Device, the "invisared-RED Elite", With a Sham Device as Therapy for the Loss of Adipose Tissue (Body Fat) and Aesthetics in Overweight Individuals"

NCT03811093

May 7, 2019

Statistical Analysis Plan

for

Invisa-RED Clinical Trial

Research Questions:

Research Question One (1): Is there a statistically significant difference in Percentage of Body Fat Lost when using an invisa-RED Technology Elite Low-level Laser Therapy (LLLT) device when compared with a sham (placebo) device in an approved and standardized clinical protocol?

Null Hypothesis One (1): There is not a statistically significant difference in Percentage of Body Fat Lost when using an invisa-RED Technology Elite Low-level Laser Therapy (LLLT) device when compared with a sham (placebo) device as a therapy in an approved and standardized clinical protocol.

Alternative Hypothesis One (1): There is a statistically significant difference in Percentage of Body Fat Lost when using an invisa-RED Technology Elite Low-level Laser Therapy (LLLT) device when compared with a sham (placebo) device as a therapy in an approved and standardized clinical protocol.

Research Question Two (2): Is there a statistically significant difference in Inches Lost when using an invisa-RED Technology Elite Low-level Laser Therapy (LLLT) device when compared with a sham (placebo) device in an approved and standardized clinical protocol?

Null Hypothesis Two (2): There is not a statistically significant difference in Inches Lost when using an invisa-RED Technology Elite Low-level Laser Therapy (LLLT) device when compared with a sham (placebo) device in an approved and standardized clinical protocol.

Alternative Hypothesis Two (2): There is a statistically significant difference in Inches Lost when using an invisa-RED Technology Elite Low-level Laser Therapy (LLLT) device when compared with a sham (placebo) device in an approved and standardized clinical protocol.

Research Question Three(3): Is there a statistically significant difference in Pounds of Body Fat Lost when using an invisa-RED Technology Elite Low-level Laser Therapy (LLLT) device as a therapy when compared with a sham (placebo) device in an approved and standardized clinical protocol?

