- Individuals with active infections, open lesions, hives, herpetic lesions, cold sores, or tattoos and permanent make-up in the area of treatment should not undergo laser light therapy.
- People who have used isotretinoin (commonly known as Accutane), tetracycline, St. John's Wort, or any photo sensitizing drugs in the last year should not undergo laser light therapy.
- Individuals with autoimmune diseases such as Lupus, Scleroderma, or Vitiligo should not undergo laser light therapy.
- Individuals who have pacemakers or other electro-stimulation devices surgically implanted should not undergo laser light therapy.
- Any insulin dependent individual should consult their physician before undergoing laser light therapy.
- All individuals considered "vulnerable" such as children, pregnant women, nursing home residents or other institutionalized persons, students, employees, fetuses, prisoners, and persons with decisional incapacity.

From the population of prospective participants screened using the above criteria, each of the approximately 40 participants selected will be randomly assigned to one of two groups; the Care as Usual Group or the Sham (placebo) Group.

Analysis:

To examine the three (3) research questions, independent sample *t*-tests using the statistical analysis program SPSS will be conducted on the three comparative data sets. Each of the three data sets will be comprised of comparative results from the two trial groups, the Care as Usual Study Group and the Sham (placebo effect) Study Group.

Data set One (1) will be the comparative Percentage of Body Fat Lost results, Data Set Two (2) will be the comparative Inches Lost results, and Data Set Three (3) will be the comparative Weight of Body Fat Lost results.

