An independent samples *t*-test is the appropriate statistical test when the purpose of research is to assess if differences exist on a continuous (interval/ratio) dependent variable by a dichotomous (2 groups) independent variable. The three continuous dependent variables to be tested are Percentage of Body Fat Lost or Gained, Weight of Body Fat Lost or Gained, and Total Inches Lost or Gained. The dichotomous independent variables for the three data sets are the invisa-RED Technology Elite Low-level Laser Therapy (LLLT) device and the sham (placebo) device, each administered as therapy in a standardized clinical protocol. The assumptions of normality and homogeneity of variance will be assessed. Normality assumes that the scores are normally distributed (bell-shaped) and will be assessed using the One-Sample Kolmogorov-Smirnov test. Homogeneity of variance assumes that both groups have equal error variances and will be assessed using Levene's Test for the Equality of Error Variances.

Each t-test will be two- tailed with the probability of rejecting the null hypothesis when it is true set at $p < 0.05$. This ensures a 95% certainty that the differences did not occur by chance. *The first t-test* using Data Set One (1) will assess if statistically significant differences exist on the dependent variable Percentage of Body Fat Lost. The second *t-test* conducted on Data Set Two (2) will assess if statistically significant differences exist on the dependent variable Inches Lost. The third *t-test* conducted on Data Set Three (3) will assess if statistically significant differences exist on the dependent variable Weight of Body Fat Lost. For each of the three data sets the independent variables are defined as an Invisia-RED Technology Elite Low-level Laser Therapy (LLLT) device and as a comparator the sham (placebo) device. Data produced by both groups will be a result of a clinical trial governed and conducted by a randomized double-blind study using an approved clinical protocol.

Reference:

Statistics Solutions. (2013). Data analysis plan: Independent Sample t-Test [WWW Document]. Retrieved from <http://www.statisticssolutions.com/academic-solutions/member-resources/member-profile/data-analysis-plan-templates/data-analysis-plan-independent-sample-t-test/>

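### Protocol and SAP test different outcomes: the SAP drops the promised body-weight test and adds pounds of body fat, with no primary outcome or multiplicity rule

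*Protocol*

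**What the plan says.** The protocol gives two outcome lists that do not match.

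- Purpose of the Study: "the change in body fat percentage, and the weight and inches lost of the two groups will be statistically analyzed". Methods and Procedures repeats this list: "the change in body fat percentage, weight, and inches lost of the two groups will be statistically analyzed to determine the efficacy". That makes three outcomes: body-fat percentage, weight and inches.
- Data Analysis and Data Monitoring, the only protocol section that names a test: "The measured weight loss and total inches lost per participant from the two groups will be statistically evaluated using an Independent T-Test". That makes two outcomes, and body-fat percentage is not one of them. The level is given as "using an Independent T-Test with a P value of .05", with no statement of one- or two-sided.

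The SAP gives a third list. Its Analysis section says: "The three continuous dependent variables to be tested are Percentage of Body Fat Lost or Gained, Weight of Body Fat Lost or Gained", and adds total inches. Research Question Three asks: "Is there a statistically significant difference in Pounds of Body Fat Lost". The matching data set is described this way: "Data Set Three (3) will be the comparative Weight of Body Fat Lost results". On the level, the SAP says: "Each t-test will be two- tailed with the probability of rejecting the null hypothesis when it is true set at" 0.05. It then presents this as 95% assurance that the differences are not due to chance.

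Neither document designates a primary outcome, a testing order with consequences, a rule for overall success, or an adjustment for several tests.

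**The concern.** The two documents cannot both be followed as they stand. Body weight is promised a t-test in the protocol and has none in the SAP. Pounds of body fat has a hypothesis and a test in the SAP but appears in no protocol outcome list. Body-fat percentage is in two protocol sections and the SAP but is missing from the protocol's own analysis section.

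The SAP's percentage of body fat lost also has no formula. It could mean the fall in body-fat percentage, as the protocol's purpose and methods sections suggest, or the share of starting fat that was lost.

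Methods and Procedures presents the trial as proof of efficacy and ties that conclusion to several outcomes together, without saying whether one, two or all must be significant. A single significant result out of three or four could then be reported as success, with a false-positive chance above the 5% stated for each test. Because the documents differ, an analyst could omit the weight test, or report whichever test succeeded, and cite a document in support.

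**Working it through.** **1. Outcome lists side by side**

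| Outcome | Protocol: Purpose; Methods and Procedures | Protocol: Data Analysis and Data Monitoring | SAP |
|---|---|---|---|
| Body-fat percentage | yes | no | yes (no formula) |
| Body weight | yes | yes | no |
| Inches | yes | yes | yes |
| Pounds of body fat | no | no | yes |

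Only inches appears in every column. The two documents together name four outcomes.

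**2. The plan's own figure**

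The SAP's 95% is the complement of its per-test level: 1 − 0.95 = 0.05. It reproduces, but for one test only.

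**3. Chance of at least one false positive**

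Inputs from the documents: three SAP tests, each two-sided at 0.05; 40 participants in two groups. Assumptions: 20 per arm (the allocation ratio is not stated), normal data, no true effect, and the same correlation between every pair of outcomes (the documents give no correlations).

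For k independent tests the chance is 1 − 0.95^k.

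- k = 3: 1 − 0.95³ = 14.26%
- k = 4: 1 − 0.95⁴ = 18.55%

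For correlated outcomes, two-sample t-tests with 20 per arm were simulated (200,000 replicates):

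| Assumed correlation | SAP's three tests | All four outcomes |
|---|---|---|
| 0.9 | 8.4% | 9.5% |
| 0.7 | 10.9% | 13.2% |
| 0.5 | 12.6% | 15.6% |
| 0 | 14.3% | 18.5% |

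Repeat simulations agreed within simulation error. The fourth test itself adds 9.5 − 8.4 = 1.1 points at correlation 0.9 and 18.55 − 14.26 = 4.3 points at 0. The rest of the excess over 5% comes from having no primary outcome or multiplicity rule.

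**4. Effect of an adjustment**

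Bonferroni over three tests uses 0.05/3 = 0.0167 each. The simulated chance of any false positive falls to 3.0% (correlation 0.9) to 4.9% (correlation 0).

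Cost, from exact noncentral-t power with 20 per arm and no dropout:

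- Difference detectable with 80% power: 0.909 SD at 0.05; 1.064 SD at 0.0167.
- Power at 0.909 SD: 80% at 0.05; 64.5% at 0.0167.

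**5. The undefined body-fat outcome**

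Take an assumed 200 lb person at 35% fat who loses 4 lb, all of it fat.

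- Starting fat: 200 × 0.35 = 70 lb.
- Final body-fat percentage: 66/196 = 33.67%, a fall of 35 − 33.67 = 1.33 percentage points.
- Share of starting fat lost: 4/70 = 5.7%.

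The two readings of the same result differ about fourfold (5.7/1.33 ≈ 4.3).

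**The case against.** The strongest reply is that the SAP fixes exactly three tests, so the four-test case is planned nowhere, and that the upper false-positive figures assume uncorrelated outcomes. Pounds of body fat and body-fat percentage measure nearly the same thing. If those two are assumed to correlate at 0.95, and each at 0 to 0.5 with inches, the three SAP tests give about 10% to 11%. This point stands in part: 14.3% and 18.5% should be read as independence values, the top of the range. But 10% to 11% is still about twice the per-test level.

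It can also be said that the protocol's weight means weight of body fat, and that the SAP's title, which is about adipose tissue, explains its choice of outcomes. The title does explain the choice, but it does not reconcile the texts. The protocol speaks of measured weight loss and lists weight separately from body-fat percentage. If fat weight was intended, the protocol needs correcting. Neither document says that the SAP takes precedence.

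The body-fat definition matters less for inference than for reporting. The protocol's wording favours percentage points, and the two readings are likely to be closely correlated. That is fair: the ambiguity mainly affects the reported size, and it would not be a major point by itself.

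Finally, the stated purpose covers weight loss and/or aesthetics, so the sponsor may want more than one confirmatory outcome. That is legitimate, but it then needs a multiplicity rule.

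**Conclusion.** The concern holds, and it should be resolved before the analysis. Followed as written, the SAP omits the body-weight test that the protocol promises, and efficacy is left to any of several unadjusted tests.

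The chance of at least one false positive is 8.4% to 14.3% for the SAP's three tests and 9.5% to 18.5% if all four outcomes are tested, against the 5% stated for each test. The mismatch between the documents accounts for about 1 to 4 points of this; the larger part comes from having no primary outcome or multiplicity rule. These figures rest on an assumed 20 per arm and assumed equal correlations from 0.9 to 0. The inconsistency between the outcome lists rests on no assumption.

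**What to change.** Make these changes before unblinding. If the groups are already unblinded, label the changes as made afterwards.

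1. Use one identical outcome list in the protocol (Purpose of the Study, Methods and Procedures, Data Analysis and Data Monitoring) and in the SAP.
2. Define the body-fat outcome as baseline minus final body-fat percentage, in percentage points.
3. Add body weight in pounds to the SAP as a tested outcome. Otherwise, remove it from every protocol list and withdraw the weight-loss conclusion in Methods and Procedures.
4. Label pounds of body fat as derived and secondary, and state its formula. Weight multiplied by body-fat percentage is the obvious one, but the documents give none.
5. Name one primary outcome at two-sided 0.05 and make the others secondary. Body-fat percentage is a natural candidate, since the protocol's purpose and methods sections and the SAP's first research question all put it first; the choice is the sponsor's. If more than one outcome is to be confirmatory, for example one for weight loss and one for aesthetics, apply Holm or Bonferroni across them (for three under Bonferroni, 0.0167 each).

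The cost is a wording amendment to both documents. No new data are needed, because the protocol already plans to analyse weight and body-fat percentage. A single primary outcome loses no power. Splitting the level over three tests raises the detectable difference from 0.91 to 1.06 SD, or lowers power at 0.91 SD from 80% to about 65%, under the same 20-per-arm, no-dropout assumption.

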## Data Storage and Security

All individuals participating in the trial will be assigned a participant number. Subsequently all clinical records and reports will reference only the participant number, ensuring that participants remain anonymous. Because of the low number of trial participants, only paper records will be maintained for all clinical and personal data. Records will be kept in locked storage and physical access will only be on a need to know basis. A participants' personal data correlating the participating individuals name and the trial participants Identifying Number will only be available to the principal investigator and trial administrator. All analytics will be performed using only data masked or redacted of any personal information.

## **Risk/Benefit Assessment**

Applying the test for the determination of risk established by the FDA Regulation referred to as the "Common Rule" found in 45 CFR 46, Subpart A the rule states;

"Minimal risk means that the probability and magnitude of harm or discomfort anticipated in the research are not greater in and of themselves than those ordinarily encountered in daily life or during the performance of routine physical or psychological examinations or tests.

We have determined that only a minimal risk is presented to participants of the trial and therefore believe a finding that the device as used in this research is Non-Significant Risk and thus qualifies for an abbreviated IDE under 21 CFR 812.2(b).

See the detail minimal risk criteria analysis below:

i. The device is NOT intended as an implant that presents a potential for serious risk to the health, safety, or welfare of a subject. *The invisa-RED Elite employs no implanted devices as part of any treatment or therapy.* 

- ii. The device is NOT purported or represented to be for a use in supporting or sustaining human life that presents a potential for serious risk to the health, safety, or welfare of a subject. *The invisa-RED Elite is only to be used as directed for weight loss therapy and aesthetics and is not represented or employed as a life sustaining device or therapy.*
- iii. The device is NOT for a use of substantial importance in diagnosing, curing, mitigating, or treating disease, or otherwise preventing impairment of human health that presents a potential for serious risk to the health, safety, or welfare of a subject. The invisa-RED Technology Elite is to be used only as directed for weight loss therapy and aesthetics. If weight loss is the goal of the therapy, the treatments should be a part of a holistic weight loss program, which may include diet, exercise, and behavior modification in the form of counseling or group therapy.
- iv. The device does NOT otherwise present a potential for serious risk to the health, safety, or welfare of a subject. The invisa-RED Elite is classified as an FDA Class II device and has passed all FDA electromagnetic compatibility (EMC) standards.

The invisa-RED Elite device employs Class 3b laser diodes in a system of "paddles" each containing multiple diodes. Class 3B lasers are hazardous for eye exposure; therefore during therapy protective eyewear is recommended for staff, the individual undergoing treatment, and any others in the room. Eye safety is further enhanced by standard invisa-RED Elite clinical procedures, which are designed to eliminate exposure of the eyes of the patient and proximate individuals to direct laser light. These clinical procedures dictate that the paddles are to be 1) placed on the area to be treated, 2) secured if required, and then and only then 3) the system is activated and treatment begun. This eliminates the chance of any direct laser light entering the eye.

Class 3B lasers can heat skin and materials but are not considered a burn hazard. However treatment protocol standards found in the users manual do recommend power settings, pulse and delay be adjusted for the patients Fitzpatrick Scale skin type; as differing skin tones result in a variable coefficient of absorption of electromagnetic energy. If these recommendations are not followed, the therapy may result in mild sunburn like effect and or skin sensitivity. Additionally each patient is asked to verbally attest to his or her comfort level at the start of each therapy session and further instructed to notify staff of any discomfort at any time. As stated in the user manual and stressed during invisa-RED Elite device Training and Certification the following contraindications and precautions for patients will apply:

- If you are pregnant, trying to get pregnant or nursing laser light therapy should be received only after the end of these conditions. There is no evidence of harm to a an unborn baby however there have been no safety tests either, so for medical legal reasons we recommend never treating areas directly over a developing child.
- Individuals with hypertension, light sensitive epilepsy, cancer, heart disease, infectious skin disease, and severe varicose veins should not use this device.
- People suffering from infectious and acute disease such as a fever should not use this device.
- People who have hemorrhagic disease, vascular ruptures, skin inflammation, or any disease of the skin should not use this device.
- People who have immune system dysfunction such as Leukemia, Hemophilia, etc., and light sensitive persons should not use this device.
- Use of laser light therapy in the ears, nose, eye, or throat is not recommended.
- Individuals with a history of melanoma, raised moles, suspicious lesions, keloid scar formation, or healing problems should not undergo laser light therapy.
- Individuals with active infections, open lesions, hives, herpetic lesions, cold sores, or tattoos and permanent make-up in the area of treatment should not undergo laser light therapy.
- People who have used isotretinoin (commonly known as Accutane), tetracycline, St. John's Wort, or any photo sensitizing drugs in the last year should not undergo laser light therapy.
- Individuals with autoimmune diseases such as Lupus, Scleroderma, or Vitiligo should not undergo laser light therapy.
- Individuals who have pacemakers or other electro-stimulation devices surgically implanted should not undergo laser light therapy.
- Any insulin dependent individual should consult their physician before undergoing laser light therapy.

All prospective participants interviewed for the trial will be vetted using the invisaRED Technologies Elite guidelines of indications and contraindications. Upon following all guidelines for indications and contraindications and employing both standard procedures for eye safety and treatment protocols, a participant's risk may best be compared to exposure to direct sunlight.

Subjects of the study receiving the invisaRED Technologies Elite therapy may receive the following health and aesthetic benefits:

- Body fat reduction through laser assisted lipolysis or \*photobiostimulation which has been shown to increase cellular metabolism
- Sculpting of targeted body areas through adipose tissue reduction and skin tightening.
- Stretch mark fading
- Elimination or reduction of cellulite
- Skin tightening and enhanced collagen production
- Increase blood flow to areas of epidermis, dermis, hypodermis, and connective tissue to stimulate cellular respiration
- Detoxification due to improved blood circulation and stimulation of lymphatic transport.

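### The protocol's statement that the paddle routine removes all chance of direct laser light reaching the eye goes further than its listed steps and its eyewear recommendation support

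*Protocol*

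**What the plan says.** All the eye-safety text is in the protocol's Risk/Benefit Assessment; the SAP does not address the subject.

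- **Hazard:** "Class 3B lasers are hazardous for eye exposure".
- **Eyewear:** as a consequence of that hazard, "during therapy protective eyewear is recommended for staff, the individual undergoing treatment, and any others in the room".
- **Procedures:** eye safety is said to be enhanced further by standard clinical procedures, "which are designed to eliminate exposure of the eyes of the patient and proximate individuals to direct laser light". The routine has three steps. The paddles are placed on the treatment area, then "secured if required, and then and only then 3) the system is activated and treatment begun".
- **Conclusion drawn from the routine:** "This eliminates the chance of any direct laser light entering the eye".
- **What rests on it:** later in the same section, provided the contraindication guidelines are followed and on condition of "employing both standard procedures for eye safety and treatment protocols, a participant's risk may best be compared to exposure to direct sunlight".

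Methods and Procedures gives each participant "nine (9) therapy sessions of 20 minutes each". Staff Training and Certification requires staff to be certified in safety and clinical procedures but does not give the content.

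**The concern.** The section names an eye hazard, gives the main personal precaution the status of a recommendation, and then states without qualification that the risk is gone. These statements do not fit together. If the routine really left no chance of exposure, the eyewear would serve no purpose. If eyewear is warranted, some chance remains.

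What is at stake is the accuracy of the risk statement. The sunlight comparison is expressly conditional on the eye-safety procedures, and the paragraph on paddles and eyewear is the only place where the documents argue eye safety. The minimal-risk determination in the same section relies in part on this discussion. Data Analysis and Data Monitoring then cites minimal risk, together with short duration, as grounds for having no detailed safety-monitoring plan. The protocol also promises candidates a thorough disclosure of risk, and an absolute statement could understate it.

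**Working it through.** This is a check of text against text. No alpha, power, effect size or event count enters it.

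**1. Timing of the listed steps.**

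| Step | When it acts | Bearing on the period after activation |
|---|---|---|
| Place paddles on the area | Before activation | None stated |
| Secure, if required | Before activation | Limits movement during the session, but only where it is applied |
| Activate and begin treatment | At activation | The list ends here |

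**2. Length of the period after activation.** From Methods and Procedures: 9 sessions × 20 minutes = 180 minutes per participant. For that time the list offers only conditional securing. It has no step for a paddle that shifts, for repositioning, or for the state of the device when a paddle is removed.

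**3. Strength of the conclusion against its support.** The section describes the procedures in two ways. One is a statement of intent, "which are designed to eliminate exposure of the eyes of the patient and proximate individuals to direct laser light". The other is a statement of achieved result, "This eliminates the chance of any direct laser light entering the eye". Three steps that end at activation, one of them conditional, can support the first. They do not establish the second.

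**4. Status of eyewear.** The section records that the users manual recommends adjusting settings to skin type, and Methods and Procedures turns the power part of that into fixed study rules. The eyewear recommendation is not treated in this way. The documents as supplied contain no section that makes eyewear a study requirement or provides for recording its use.

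**5. What depends on it.** The sunlight comparison carries the condition "employing both standard procedures for eye safety and treatment protocols". If those procedures are described more strongly than the text supports, the comparison inherits the overstatement.

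**The case against.** The strongest reply is that the section puts eyewear first and adds the routine to it. The routine is not offered as a reason for making eyewear optional, and a site that follows the recommendation has eyewear on everyone in the room. The section also summarises standard procedures within a risk assessment and does not claim to reproduce them in full. A training manual, a user manual and a staff certification all exist, and any of them may deal with movement, repositioning and switching off. All of this stands. It limits the point to what the protocol text shows, but it does not rescue the unqualified sentence, because the protocol does not cite those sources for the rest of the session.

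A reader might infer more, and the documents do not support it:

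- **That the routine protects only at the moment of switching on.** A secured paddle also limits exposure during the session, so this overlooks the second step.
- **That eye safety is in fact not achieved.** The manuals and certification content are not in the documents. The property is asserted and not demonstrated, which is different from being shown to fail.
- **That eyewear use would drift apart between groups and reveal allocation.** Nothing in the documents indicates this. The sham is meant to appear to the operator to work like the active device, and the groups attend on different days with separate staff.
- **That total session hours measure the hazard.** They measure session time. Removing a paddle is hazardous only if the device still emits, and the documents do not say whether it does.
- **That the absence of a safety-monitoring plan rests on this sentence.** Short duration is a second stated ground, and the minimal-risk determination lists four criteria, of which the last cites device class and electromagnetic compatibility.

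**Conclusion.** The point holds as a correction to safety wording. Beside a stated eye hazard and an eyewear recommendation, the protocol claims that direct exposure is excluded altogether, and its listed steps end at activation with securing left conditional. The claim is not supported by the protocol text, and the sunlight comparison that depends on it needs the same adjustment.

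The size is minor. The text leaves 180 minutes per participant without a listed eye-safety step beyond conditional securing, but the documents give no rate of paddle displacement or of exposure, so no probability of harm follows. The endpoints, *t*-tests, significance level and planned number of participants are untouched.

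The conclusion assumes only that the protocol text is read as it stands. If the user manual or certification covers the rest of the session, citing it would close the procedural gap. The unqualified sentence would still need to be reconciled with the recommendation to wear eyewear.

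**What to change.** In the Risk/Benefit Assessment:

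1. Reconcile the hazard statement, the status of eyewear and the absolute sentence. Replace the latter with wording that the listed steps support, for example that the routine is designed to reduce the chance of direct laser light entering the eye.
2. Restate the sunlight comparison to match, since it is conditional on these procedures.
3. State the eyewear precaution, already recommended for everyone present, as a definite study procedure. It should be the same in both groups, as blinded staff cannot know which device they hold, and the same in the post-blind sessions, which use the functional device.
4. State or cite the device procedure that governs the rest of the session and paddle removal. Its content is for the sponsor to supply, and this review does not propose one.

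The cost is a few sentences of protocol wording, a check of the manual and certification content, and consistent eyewear practice at each session. The downside is a slightly less favourable risk statement. The SAP needs no change.
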